This section has been added to this study SAP following the completion of Phase I in all geographies. While the initial investigation plan intended for the study to be conducted in two phases across multiple geographies, only one geography has opted to complete both phases of the study. The geographies that have completed Phase I of the study are CEE, Latin America and South Asia. Only South Asia has proceeded into Phase II of the study with sites in both India and Bangladesh participating in both phases. CEE and Latin America both terminated their participation in IMPROVE Brady after completing Phase I of the study. Accordingly, planned statistical analyses that were going to investigate study objectives within geography or country can no longer be performed. Therefore, for any analysis comparing phases, it will be performed on the South Asia geography only. Analyses by site within the South Asia geography will only include sites enrolling in both Phase I and Phase II.

This document is electronically controlled. Printed copies are considered uncontrolled.

Confidential

7. Determination of Sample Size

Calculations of Phase II Sample Size Adaptation

The planned sample size in Phase II is up to 1100 enrollments. This sample size assumes that, in Phase I, 20% of enrolled subjects obtain an SND diagnosis and that 10% of subjects with an SND diagnosis then go on to receive indicated therapy with an IPG. This sample size also assumes that 10% of enrolled subjects will be lost to follow-up. The sample size in Phase II will be adapted, however, if the results from Phase I within each geography differ from the original assumptions about diagnosis and implant rates. The adaptation is described below.

Summary

Enrolling 500 subjects in Phase I and 1000 subjects with complete follow-up in Phase II powers the study to detect increases in the SND percentage of 9% or greater. The study is also powered to detect an increase in the IPG implant percentage by 15%. This assumes that the Phase I SND percentage is 20% or greater and that the percent of diagnoses does not decrease in Phase II.

Synopsis of Phase II Preliminary Power and Sample Size Calculations

For Phase II, we will outline many different possible scenarios and the sample sizes required for each. Actual Phase II calculations will depend on what is observed in Phase I within each geography.

Section 4.1 Primary objective #1 for SND

The following assumptions are made for all calculations.

Assumptions:

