1. 90% power and type I error of 0.05
2. Phase I enrolled 500 subjects with complete follow-up
3. Overall goal is 2:1 sampling for Phase II versus Phase I
4. Calculation via methods in Fleiss JL, Tytun A, Ury HK (1980): A simple approximation for calculating sample sizes for comparing independent proportions. *Biometrics* 36:343–6.

Table 2. Subjects Required to Observe Changes in SND Diagnosis

SND % Phase I	SND % Phase II	Phase II Subjects	Higher SND % Phase II	Phase II Subjects
------------------	-------------------	----------------------	--------------------------	----------------------

This document is electronically controlled. Printed copies are considered uncontrolled.

Confidential

10%	20%	N=405	25%	N=203
20%	30%	N=593	35%	N=279
30%	40%	N=717	45%	N=327
40%	50%	N=778	55%	N=347
45%	55%	N=785	60%	N=346
50%	60%	N=776	65%	N=338
60%	70%	N=711	75%	N=302
70%	80%	N=582	85%	N=237
80%	90%	N=390	95%	N=144

There is clear power to attain the first primary objective with 873 subjects or fewer in Phase II, accounting for 10% attrition.

Section 4.2 Primary objective #2 for IPG implants

Scenario 1 -- Additional assumptions:

1. No change in SND diagnosis between Phase I and Phase II, i.e., the first primary objective is not met.
2. Futility is assumed when more than 1000 subjects with complete follow-up are needed for Phase II. Areas of futility are not included in **Error! Reference source not found.** and **Error! Reference source not found..**

Table 3. For SND diagnosis rates less than 50%

	IPG % Phase I	IPG % Phase II	Phase II Subjects Needed	Accounting for Attrition	CI width for IPG % with Half of Phase II Data
10% SND = 50 SNDs	80%	95%	>1000	>1000	0.06
	85%	100%	856	952	0.03
20% SND = 100 SNDs	5%	20%	769	855	0.18
	10%	25%	1013	1126	0.17
	15%	30%	>1000	>1000	0.16

This document is electronically controlled. Printed copies are considered uncontrolled.

Confidential

	70%	85%	>1000	>1000	0.07
	75%	90%	968	1076	0.07
	80%	95%	717	797	0.06
	85%	100%	428	476	0.03
30% SND = 150 SNDs	5%	20%	513	570	0.18
	10%	25%	676	752	0.17
	15%	30%	814	905	0.16
	20%	35%	929	1033	0.16
	25%	40%	1021	1135	0.15
	30%	45%	>1000	>1000	0.15
	55%	70%	>1000	>1000	0.14
	60%	75%	1004	1116	0.14
	65%	80%	908	1009	0.13
	70%	85%	788	876	0.13
	75%	90%	645	717	0.12
	80%	95%	478	532	0.10
40% SND = 200 SNDs	85%	100%	286	318	0.08
	5%	20%	385	428	0.18
	10%	25%	507	564	0.17
	15%	30%	611	679	0.16
	20%	35%	697	775	0.16
	25%	40%	766	852	0.15
	30%	45%	817	908	0.15
	35%	50%	850	945	0.15

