	25%	40%	341	379	0.15
	30%	45%	363	404	0.15
	35%	50%	378	420	0.15
	40%	55%	385	428	0.15
	45%	60%	384	427	0.14
	50%	65%	376	418	0.14
	55%	70%	359	399	0.14
	60%	75%	335	373	0.14
	65%	80%	303	337	0.13
	70%	85%	263	293	0.13
	75%	90%	215	239	0.12
	80%	95%	160	178	0.10
	85%	100%	96	107	0.08

Additional calculations:

If the Phase II data is divided into two pieces, then there would be, ideally, an equal number of SND diagnoses and number treated with IPG in each piece. The following table describes the width of the confidence intervals around the IPG proportions estimated in Phase II, the width around the point estimate for one half of the Phase II enrollments and the width around the difference in the proportions from the two halves of Phase II.

Table 5. For SND diagnosis rates greater than 50%

IPG % Phase II	Number of SND dx in Phase II	CI width for IPG % with Half of Phase II Data	CI width for Comparison of IPG % Between Two Halves of Phase II
20%	154	0.19	0.26
25%	203	0.18	0.24
30%	245	0.17	0.23
35%	279	0.16	0.22
40%	307	0.16	0.22
45%	327	0.16	0.22
50%	340	0.16	0.21
55%	347	0.15	0.21
60%	346	0.15	0.21
65%	338	0.15	0.20
70%	323	0.15	0.20
75%	302	0.14	0.20
80%	273	0.14	0.19
85%	237	0.14	0.18
90%	194	0.13	0.16
95%	144	0.11	0.13

To compare the SND proportion between these two pieces, we have a confidence interval total width of 12% (absolute range) or less. To compare the IPG proportion between these two pieces, we have a confidence interval total width of 26% (absolute range) or less.

Futility examples

Suppose that the SND percentage is 10% and that less than 85% of those indicated will implant. Assuming 500 patients in Phase I, we will need 2,520 patients in Phase II to see an increase in the implant rate from 10% to 30%. This is an example of a scenario where we may decide not to move forward into Phase II.

This document is electronically controlled. Printed copies are considered uncontrolled.

Confidential

Suppose that the SND percentage is 5% and that 5% of those indicated will implant. Assuming 500 patients in Phase I, we will need 5,440 patients in Phase II to see an increase in the implant rate from 5% to 30%. This is another example of a scenario where we may decide not to move forward into Phase II.

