Suppose that the SND percentage is 20% and that 40% of those indicated will implant. Assuming 500 patients in Phase I, we will need more than 10,000 patients in Phase II to see an increase in the implant rate from 40% to 55%. If there are 910 patients in Phase II, this is sufficient to detect an increase in the implant rate from 40% to 60%.

8. Statistical Methods

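### SAP Section 7: the Phase II sizes in Tables 2–4 are not those for the stated 500-subject Phase I, and the claimed power for a 15-point rise in IPG use at 20% SND is contradicted by the section's own table and example

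*SAP*

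**What the plan says.** SAP Section 7 is presented as the way the Phase II size will be adapted once Phase I is known. Its assumptions for all calculations include "90% power and type I error of 0.05", "Phase I enrolled 500 subjects with complete follow-up" and an overall goal of two Phase II subjects per Phase I subject.

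- **Table 2** gives Phase II sizes for a rise in SND diagnosis. The text after it concludes: "There is clear power to attain the first primary objective with 873 subjects or fewer in Phase II, accounting for 10% attrition".
- **Tables 3 and 4** give Phase II sizes for a 15-point rise in IPG use. Their row blocks are labelled with the SND count that a Phase I of 500 would yield (100 SNDs at 20%, 250 at 50%, 450 at 90%).
- **The futility rule** for those tables is "Futility is assumed when more than 1000 subjects with complete follow-up are needed for Phase II", and cells in that region are said to be left out.
- **The Summary** relies on 500 Phase I and 1,000 Phase II completers and states "The study is also powered to detect an increase in the IPG implant percentage by 15" per cent, provided Phase I SND is at least 20%. That statement names no IPG baseline. The start of the section assumes 10%.
- **The futility examples** say, at 10% SND, "we will need 2,520 patients in Phase II to see an increase in the implant rate from 10% to 30" per cent and, at 20% SND, "we will need more than 10,000 patients in Phase II to see an increase in the implant rate from 40% to 55" per cent. Two further examples give 5,440 (5% SND, IPG 5% to 30%) and 910 (20% SND, IPG 40% to 60%).
- **SAP 8.5.2.2** gives the detectable IPG increase as 16 points, for 100 against 200 SND subjects and a 10% baseline.

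**The concern.** Once Phase I is finished its size is a fixed number, and the only question is how many Phase II subjects to add. A table that lets Phase I shrink or grow with Phase II answers a different question. Tables 3–4 show this on their face: for IPG 10% to 25%, the rows labelled 100, 250 and 450 Phase I SNDs all imply the same 203 or so Phase II SND subjects (1,013 × 0.2, 406 × 0.5, 226 × 0.9). The labelled Phase I count has no effect.

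The Summary is the sentence a reader will take away about power for the second primary objective. If it holds only at some IPG baselines and names none, it promises power that the design does not have over much of the range. The futility rule is applied to the same figures, so an error in them can also affect whether a geography continues.

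**Working it through.** **Inputs (SAP Section 7).** Power 0.90; type I error 0.05, taken as two-sided because the section does not say and two-sided reproduces the tables; Phase I = 500; 2:1 goal; same SND rate in both phases for Tables 3–4; 10% attrition. z values 1.960 and 1.2816. Formula: pooled-variance comparison of two proportions without continuity correction.

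**Step 1. Reproduce Table 2 as a free 2:1 design.** With r = 2 and p̄ = (p1 + r·p2)/(1 + r):

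n1 = [1.960·√((r+1)·p̄(1−p̄)) + 1.2816·√(r·p1(1−p1) + p2(1−p2))]² / [r·(p2−p1)²], and n2 = r·n1.

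For 20% to 30%: p̄ = 0.2667; the bracket is 1.960·√0.5867 + 1.2816·√0.53 = 1.501 + 0.933 = 2.434; n1 = 5.925/0.02 = 296.3; n2 = 592.5, which rounds up to the printed 593. The whole 10-point column comes out as 405.0, 592.5, 716.7, 777.6, 784.4, 775.4, 710.1, 581.7 and 389.9, which match the printed 405 to 390. The 593 is therefore paired with a Phase I of about 297, not 500. A continuity correction would give 624 for this row and matches no Table 2 cell.

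**Step 2. Hold Phase I at 500.** Find the smallest n2 with

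1.960·√(p̄(1−p̄)(1/n1 + 1/n2)) + 1.2816·√(p1(1−p1)/n1 + p2(1−p2)/n2) ≤ p2 − p1, where p̄ = (n1·p1 + n2·p2)/(n1 + n2).

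For 20% to 30% with n1 = 500 and n2 = 319: 0.0599 + 0.0401 = 0.1000.

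| SND contrast | Printed N | Phase I fixed at 500 |
|---|---|---|
| 10% to 20% | 405 | 173 |
| 20% to 30% | 593 | 319 |
| 30% to 40% | 717 | 454 |
| 45% to 55% (largest) | 785 | 549 |
| 80% to 90% | 390 | 186 |
| 20% to 35% | 279 | 109 |

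The 10-point column runs 173–549 instead of 390–785, and the 15-point column 57–150 instead of 144–347. The maximum with attrition is 549/0.9 = 610, against 785/0.9 = 873.

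**Step 3. Tables 3–4.** The 2:1 formula for IPG 10% to 25% gives n2 = 202.55 SND subjects. Divided by the SND rate this is 1,012.8, 405.1 and 225.1 at 20%, 50% and 90% SND, printed as 1013, 406 and 226. For the fixed version, n1 = 500 × SND rate, and the Phase II SND count is rounded up before dividing.

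| SND | IPG contrast | Printed | Phase I fixed |
|---|---|---|---|
| 40% | 40% to 55% | 866 | 273/0.4 = 683 |
| 50% | 40% to 55% | 693 | 215/0.5 = 430 |
| 90% | 40% to 55% | 385 | 155/0.9 = 173 |
| 90% | 10% to 25% | 226 | 71/0.9 = 79 |
| 20% | 10% to 25% | 1013 | 209/0.2 = 1,045 |
| 30% | 25% to 40% | 1021 | 320/0.3 = 1,067 |
| 30% | 60% to 75% | 1004 | 304/0.3 = 1,014 |

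Unrounded SND counts give 1,041 and 1,064 for the fifth and sixth rows. A printed figure is too low only when its implied Phase I exceeds 500, that is, when it exceeds 1,000. The last three rows are those cells.

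**Step 4. The futility examples use the fixed method.** With Phase I SND counts of 50, 25 and 100, the fixed method gives 252/0.10 = 2,520, 272/0.05 = 5,440 and 182/0.20 = 910, exactly as printed. The free 2:1 method would give about 1,250, 1,420 and 967. For 40% to 55% with 100 Phase I SNDs, an unlimited Phase II gives (0.15 − 1.960·√(0.55·0.45/100))/√(0.40·0.60/100) = 1.07, so power stops at about 0.86 and there is no finite solution. That fits the printed statement of more than 10,000. The tables' method would give about 1,730.

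**Step 5. The 15-point claim at 20% SND.** 500 and 1,000 completers give 100 and 200 SND subjects.

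| IPG baseline | Normal-approximation power | Exact Fisher power | Table 3 at 20% SND |
|---|---|---|---|
| 5% | 0.964 | 0.966 | 769 |
| 10% | 0.896 | 0.890 | 1013 (1126 with attrition) |
| 15% | 0.830 | 0.823 | >1000 |
| 20% | 0.778 | 0.763 | omitted |
| 40% | 0.690 | 0.678 | omitted |
| 70% | 0.849 | 0.834 | >1000 |
| 75% | 0.909 | 0.899 | 968 |

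**The case against.** The best defence is that nothing was miscalculated. The 2:1 goal is listed beside the 500-subject assumption, and it has a stated purpose: to examine temporal drift (SAP Sections 5 and 8.4) and to inform secondary objectives (Protocol Section 11). The tables are called preliminary. Nearly every printed cell errs towards more subjects. The three that are too low are off by only 1% to 5% and already lie above the 1,000 limit, so no continuation decision turns on them. On the 15-point claim, the planning baseline of 10% appears just above the Summary; at that baseline the miss is 1,013 against 1,000, and SAP 8.5.2.2 already gives 16 points. The larger shortfalls occur at baselines that the SAP itself shows as futile. Finally, the study is described as exploratory, South Asia had entered Phase II when this version was written, and no test or analysis set depends on these tables.

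Much of this stands as to consequence: the understatement is small, and the Summary claim is met at a 5% baseline and met or nearly met from 75% up. It does not remove the error. With 500 in Phase I, a 2:1 ratio can only mean 1,000, so a printed 593 satisfies neither assumption as a pair. The section's own examples use the other method without saying so. The Summary ties its claim to the SND rate alone, and that claim fails across IPG baselines of about 15% to 70%.

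**Conclusion.** The point holds in both parts.

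First, Tables 2–4 are correct for a free 2:1 design but do not answer the question Section 7 poses. For a Phase I of 500, Table 2 overstates the Phase II need by 204 to 274 subjects in the 10-point rows shown above (for example 593 − 319 = 274 and 390 − 186 = 204). Tables 3–4 overstate it in every printed numeric cell at or below 1,000 and understate it slightly in three cells above 1,000. The futility examples follow the fixed-Phase I method, so the section is internally inconsistent.

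Second, at 20% SND the design has 90% power for a 15-point IPG rise only at low or high baselines. It falls marginally short at the planned 10% (0.89 to 0.90) and clearly short from about 15% to 70% (0.68 to 0.85).

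These results assume a two-sided 0.05 test, the pooled formula without continuity correction, and exactly 500 Phase I completers. A continuity correction moves the fixed-Phase I figures up modestly (20% to 30%: 347 instead of 319) and does not reconcile them with the tables. The practical effect is on planning and stated power, not on the estimators or tests.

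**What to change.** 1. Recompute Tables 2–4 with Phase I held at its size, as the futility examples already do. SAP Section 6 says Phase I is complete, so the achieved enrolled and SND counts can replace the notional 500. If the 2:1 ratio is kept for temporal drift and the secondary objectives, say that it governs, label the present columns as free 2:1 sizes, and show the fixed-Phase I column beside them. State the sidedness and that no continuity correction is used.
2. Correct the sentence after Table 2: with Phase I at 500, the largest size after 10% attrition is 610, not 873.
3. Replace the Summary claim with one that names the IPG baseline: at 20% SND, about 16 points if the Phase I IPG rate is 10% (agreeing with SAP 8.5.2.2), and more at mid-range rates, about 20 points at 40% (agreeing with the SAP's 910 example).
4. Apply the futility limit of 1,000 completers to the listed cells 1004, 1013 and 1021, or change the limit.

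The cost is recalculation and SAP text. The correction adds no subjects, and most cells need fewer.

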8.1. Study Subjects

8.1.1. Disposition of Subjects

Subjects will be summarized with a STROBE diagram, including number of

- Enrolled subjects
- Subjects meeting/not meeting inclusion/exclusion criteria and lost to follow-up
- Subjects per geography (global analyses)
- Subjects with SND diagnosis (per diagnosis selected on eCRF)
- Subjects for whom investigator selected as indicated for a device on the treatment CRF
- Subjects implanted with an IPG during follow up

8.2. General Methodology

8.2.1. Special Considerations

The study will have an enrollment restriction. The maximum number of subjects to be enrolled at any given study center is 20% of the expected sample size in that geography; 20% of 1650 subjects equals 330 subjects per study center.

Sample size calculations will account for an attrition rate in the study of 10%.

An analysis will be built to examine temporal confounding. Since the study design does not randomize the treatment and control subjects it is possible that the time elapsed over Phase I and Phase II of the study will confound the results. To examine the possibility of temporal confounding, an interrupted time series regression analysis will be performed. This analysis will adapt Rubin's causal model for rate parameters.

This document is electronically controlled. Printed copies are considered uncontrolled.

Confidential

Rubin's causal model for linear outcome Y is $Y = \beta_0 + \beta_1 X + \beta_2 D$, where X is time and D is a dummy variable for group assignment, before and after intervention. To adopt this model for rate parameters estimated in the primary objectives of the study, the model to be fit is $\log(Y) = \beta_0 + \beta_1 X + \beta_2 D + \log(Z)$ where Y is a binary response to indicate an SND diagnosis and Z is the amount of subject follow-up. The same model will also be fit to model the rate of IPG treatment. If an association is seen by testing β_1 , then temporal confounding exists.

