4.3 Study Design

There are two phases to IMPROVE Brady:

Phase I: This phase of the study serves as a control period. During Phase I physicians will assess and treat subjects per their site's standard care practice. Enrollment for Phase I is anticipated to occur for approximately 12 months but will continue until 550 subjects have been enrolled for the geography/country. For subjects enrolled during Phase I, collection of diagnostic assessment and implant data will be complete 6 months after the last enrollment for the geography/country. At that time, all Phase I subjects will be exited.

If a center becomes active after the geography/country enrollment goal for Phase I has been met or the center did not enroll at least 10 subjects before Phase I enrollment stopped then the center will enroll Phase I subjects until 10 subjects have been enrolled at that center. Once 10 subjects have been enrolled at the center, enrollment will stop and the subjects will be followed for a maximum of 6 months and exited from the study.

Phase II:

The objective of the IMPROVE Brady study is to provide investigators with comprehensive resources that may be adapted by the Principal Investigator and his/her colleagues to create a practice specific process improvement intervention to improve the quality of care for patients.

At the completion of Phase I, the Principal Investigator and co-investigators will complete an educational workshop and be given access to the IMPROVE Brady toolkit. In addition, the Principal Investigator and his/her colleagues are encouraged to adapt tools from the IMPROVE Brady toolkit to create a practice specific process improvement intervention.

Immediately following completion of the educational workshop, study investigators will receive written authorization from Medtronic that they are authorized to enroll subjects in Phase II. Enrollment during this phase is anticipated to occur for approximately 18 months per geography/country.

[figure not shown]
The IMPROVE Brady process improvement intervention toolkit may include an education workshop, diagnostic algorithm(s), patient video and tools for investigators to educate their patients on their disease state, available therapy options, and benefits and risks associated with the therapy options.

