During Phase II a patient survey assessing the subject's quality of life and functional status, will be completed by subjects meeting an SND indication for pacing therapy and being implanted with a market released pacemaker from the Medtronic family of devices. The patient survey must be completed before the implant procedure and again at 6 months post-implant.

The caregiver of the subject being implanted with the market released pacemaker from the Medtronic family of devices will be asked to participate in a caregiver survey. The purpose of the survey is to assess how providing care to the person receiving the pacemaker impacts the caregiver. Prior to completing the survey an Informed Consent or Patient Data Release will need to be signed by the caregiver. The caregiver survey will be completed prior to the implant procedure and again at 6 months post-implant. The same caregiver must complete the pre and post implant surveys of the same patient.

For subjects enrolled during Phase II collection of diagnostic assessment data will be complete 6 months after last enrollment for the geography/country. At that time, any subjects without a diagnosis will be exited from the study. Collection of implant data will be complete 6 months after the last Phase II diagnosis for the respective geography/country. Any subjects not implanted by the end of the 6 months will be exited from the study. The Geography/country study timeline (Figure 2) depicts the geography/country timeline.

Figure 2: Geography/country study timeline

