5. Subject has completed the final scheduled follow-up visit (in Phase II).

This document is electronically controlled. Printed copies are considered uncontrolled.

Confidential

6. Geography/country completion of Phase I follow-up
7. Study closure

The IMPROVE Brady study will not use randomization to divide subjects into treatment groups, but rather will implement a two-phase design. Since the current rates of SND diagnosis and IPG therapy are not known, it is not feasible to construct a study with two simultaneous treatment arms and adequately power the comparison. Thus, the IMPROVE Brady study will have two sequential phases. In the first phase, the control phase, we expect to obtain baseline measurements for key variables including the rate of SND diagnosis and the rate of implantation of an IPG in subjects with an SND diagnosis. Once phase one enrollment is complete for a geographic region, patients will be followed for six months and then will be exited from the study. Physicians at participating centers will then receive an educational intervention and comprehensive disease state management tools on the adoption of ACC/AHA/HRS and ESC indications. In the second phase, the experimental phase, patients will have scheduled follow-up to collect questionnaire data if they are implanted with an IPG manufactured by Medtronic.

Each of the geographies currently participating has differing rates of SND diagnosis and implantation. Early enrollment figures anticipate the accrual of 60 subjects per month per geography, to be obtained through ten or more clinical centers. Given that baseline disease and treatment rates differ by geography, we anticipate that statistical analysis will stratify by geography and thus sample size calculations shall be stratified also. It may also be necessary to look more finely at rates by site within geography. All primary and secondary objectives will be investigated within each geography, in addition to the overall testing of primary and secondary objectives, which will include geography as a covariate.

Baseline IPG Rates

Table 1 shows WHO estimates of new implantation rates per million people (Mond *et al*)

Table 1

Region	Country	Centers	New Implants/Million (2005)
Eastern Europe	Russia	99	101
Asia	China	417	13
	Hongkong	20	157
	South Korea	100	29
	Taiwan	78	119
Southeast Asia	India	417	7
	Singapore	10	91
	Thailand	46	22

This document is electronically controlled. Printed copies are considered uncontrolled.

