8.5.1.1. Analysis Methods

A. Statistical Methodology

To compare the proportion of subjects with an SND diagnosis pre-intervention (Phase I) to the proportion post-intervention (Phase II), a chi-square test will determine statistical significance. The proportion of subjects diagnosed will be evaluated at multiple time points because the time to diagnosis is expected to vary by geography. Thus, times are pre-specified starting at 6 months and any additional 6-month interval thereafter for which there is sufficient follow-up data available to compare study phases.

Proportions calculated at all available time points will be reported. Additionally a Poisson regression will compare the average number of subjects with an SND diagnosis in Phase I and Phase II where the subject time in study is treated as an offset in the model. The above described tests will be performed only for subjects in the South Asia geographical region as per section 6.

[REDACTED]

[REDACTED]

This document is electronically controlled. Printed copies are considered uncontrolled.

Confidential

[REDACTED]

[REDACTED]

[REDACTED]

B. Determination of Patients/Data for Analysis

All subjects that are enrolled in the study will be included in the determination of the proportion estimates. The proportion estimates will be calculated based on information from fixed time points at 6 months of follow-up, 12 months of follow-up, and any additional 6-month interval thereafter for which there is sufficient follow-up data available to compare study phases. The number of subjects that obtain an SND diagnosis by pre-specified time point $t = 6, 12, \text{ etc.}$, is included in the numerator and the number of subjects enrolled is included in the denominator.

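### The temporal-confounding test in SAP 8.2.1 can reject far more often than 5% with no time trend, because follow-up shortens with enrolment date within each phase

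*SAP*

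**What the plan says.** SAP 8.2.1 proposes an interrupted time series model, log(Y) = β0 + β1·X + β2·D + log(Z), to examine whether elapsed time confounds the phase comparison. There "X is time and D is a dummy variable for group assignment, before and after intervention", and "Y is a binary response to indicate an SND diagnosis and Z is the amount of subject follow-up". The same model is to be fitted for IPG treatment. The reading rule carries no condition: "If an association is seen by testing β_1 , then temporal confounding exists".

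Z is not said to stop at diagnosis. The Poisson comparison in SAP 8.5.1.1 is worded in the same spirit: "where the subject time in study is treated as an offset in the model".

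Follow-up ends on a common date in each phase. For Phase I, Protocol 4.3 says "collection of diagnostic assessment and implant data will be complete 6 months after the last enrollment for the geography/country", and SAP section 5 agrees: "Once phase one enrollment is complete for a geographic region, patients will be followed for six months and then will be exited from the study". For Phase II, Protocol 4.3 says "collection of diagnostic assessment data will be complete 6 months after last enrollment for the geography/country". Protocol 5.7 and SAP section 5 also let subjects leave sooner, for example when there is no SND indication or no pacing is planned. Protocol 5.7 makes this permissive, so the share leaving early is not fixed.

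SAP 8.2.1 gives no origin or unit for X, no fixed follow-up window, no term for time since enrolment and no check that the diagnosis hazard is constant.

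**The concern.** A log(Z) offset is neutral only if the event rate per unit of Z is the same for short and long follow-up. A subject is diagnosed once. If Z runs on after diagnosis, or if diagnoses come mostly early in the work-up, long follow-up adds person-time with few or no events. The apparent rate is then low for subjects enrolled early in a phase and high for those enrolled late. Because follow-up resets at the start of Phase II, the apparent rate drops there and climbs again.

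The model can describe that saw-tooth only as a positive β1 and a negative β2. The check could therefore announce temporal confounding where practice did not drift, and its phase coefficient could have the wrong sign. In a non-randomised before/after study, now compared in South Asia only (SAP section 6), that could wrongly cast doubt on a real effect.

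**Working it through.** **Inputs.** Phase I enrols for about 12 months and Phase II for about 18, each closing 6 months after last enrolment (Protocol 4.3). Maximum follow-up is 12 + 6 = 18 falling to 6 months, then 18 + 6 = 24 falling to 6 months. Sample sizes of 500 and 1000, 20% diagnosed at 6 months, alternative 28%, and type I error 0.05 come from SAP 8.5.1.2. Assumed: X is enrolment date, accrual is uniform over months 0-12 and 18-36, there is no random loss, and the test is two-sided.

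**The plan's own rate.** 0.20/0.5 = 0.40 and 0.28/0.5 = 0.56 per person-year, as stated. This credits everyone with the full 6 months, so person-time does not stop at diagnosis. The constant hazard giving 20% at 6 months is −ln(0.80)/0.5 = 0.446. The documents state no size or power for the β1 test.

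**By hand: no trend, no effect, Z to phase close.** Apparent rate = proportion diagnosed / follow-up in years.

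| | Phase I first | Phase I last | Phase II first | Phase II last |
|---|---|---|---|---|
| Constant hazard | (1−0.8³)/1.5 = 0.325 | 0.40 | (1−0.8⁴)/2 = 0.295 | 0.40 |
| All diagnoses within 6 months | 0.20/1.5 = 0.13 | 0.40 | 0.20/2 = 0.10 | 0.40 |

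With a half-year gap between the last Phase I and first Phase II enrolment, β2 ≈ ln(first Phase II rate / last Phase I rate) − 0.5·β1.

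- Constant hazard: the slope is ln(0.40/0.325)/1 = 0.21 per year in Phase I and ln(0.40/0.295)/1.5 = 0.20 in Phase II. Then β2 ≈ −0.30 − 0.10 = −0.40, and exp(β2) ≈ 0.67.
- All within 6 months: the slope is ln(0.40/0.133)/1 = 1.10 and ln(0.40/0.10)/1.5 = 0.92. Taking 0.92, β2 ≈ −1.39 − 0.46 = −1.85, and exp(β2) ≈ 0.16.
- Constant hazard with a true rise to 28%: the first Phase II rate is (1−0.72⁴)/2 = 0.366. With the simulated slope of 0.27, β2 ≈ ln(0.366/0.40) − 0.135 = −0.22, and exp(β2) ≈ 0.80.

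**Simulation.** Poisson fit of the SAP model, 2,000 trials per cell (800 for the 0.48 entry), Wald test at 1.96, nobody leaving early:

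| Diagnosis timing | β1 rejects, Z to close | Median exp(β2), no effect | Median exp(β2), true 20% to 28% | β1 rejects, Z stopped at diagnosis | β1 rejects, 6-month window |
|---|---|---|---|---|---|
| Constant hazard | 46% | 0.66 | 0.77 | 5% | 4.4% |
| Declining hazard (20/27/32% at 6/12/18 months) | 99% | 0.37 | 0.48 | 87% | 5.6% |
| All within 6 months | 100% | 0.17 | 0.24 | 100% | 4.9% |

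All but the last two columns use Z to phase close. All rejection columns have no trend and no effect; the window column uses Z = time to diagnosis or 6 months. A separate simulation with 550/1100 subjects agrees: 47% and 100% with Z to close, and about 6% with constant hazard and Z stopped at diagnosis. With 10 and 20 months of enrolment, also envisaged in SAP section 5, the first column becomes 53%, 99% and 100%.

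**Early exit.** SAP section 7 assumes 10% of SND subjects receive an IPG. Let the other 90% leave within about a month of diagnosis and the implanted 10% about 6 months later. β1 rejection, Z = time in study, no trend:

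| Share of those undiagnosed at 6 months who leave early | 0% | 50% | 80% | 100% |
|---|---|---|---|---|
| Constant hazard | 4% | 10% | 11% | 3% |
| Declining hazard | 87% | 79% | 48% | 3% |
| All within 6 months | 100% | 98% | 74% | 4% |

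A differently built exit model (550/1100) shows the same dependence. When 50% or 80% of subjects without SND leave and diagnosed subjects stay, it gives 24% and 10% (constant hazard) and 100% (early-concentrated). When diagnosed subjects also leave, it gives 2-6% and 97% falling to 78%.

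**The case against.** Falling follow-up is not enough by itself. With constant hazard and Z stopped at diagnosis, follow-up falls exactly as above and the test holds its level. Under constant hazard the whole defect is post-diagnosis time in the offset. Nor do the documents give any distribution of time to diagnosis. The early-concentrated shapes are assumptions, and the most extreme sits poorly with SAP 8.5.4.1, which tabulates diagnoses at 6-12 and 12-18 months. If nearly everyone leaves at a decision, as Protocol 5.7 and SAP section 5 permit, the distortion largely goes. All of this stands, and it makes the point conditional.

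It does not remove the point, because the plan secures none of these conditions. Z is described as follow-up, exit is optional, and Protocol 4.3 expects undiagnosed Phase II subjects to remain until the cut-off. The reading rule has no qualification.

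Three stronger readings are tempting and not supported:

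- That this is the plan's only check on drift. SAP section 5 gives temporal drift as a reason for the 1:2 ratio, SAP section 7 sizes a comparison of the two halves of Phase II, and some analysis text is redacted.
- That the trial would report harm. SAP 8.2.1 attaches a meaning to β1 only. The main comparison of proportions is a chi-square test at fixed time points, in a study that SAP 4.1 calls exploratory.
- That the check would usually misfire. This depends on exit shares and a hazard shape that the documents do not give.

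**Conclusion.** The concern holds in conditional form. As SAP 8.2.1 is worded, a significant β1 cannot be read as temporal confounding, because the test can reject with no calendar trend. With Z run to phase close, rejection is about 46% under constant hazard and 99-100% if diagnoses concentrate early, against a nominal 5%. In the same setting a true rise from 20% to 28% gives a median exp(β2) of about 0.77 to 0.24, below 1 where the truth is about 1.4 (0.28/0.20).

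Two things are needed: Z running past diagnosis or a hazard that falls with time since enrolment, and enough subjects staying to cut-off. Without them the test is close to nominal. With partial early exit the rate runs from roughly 10% (near nominal in some constant-hazard runs) to 100%.

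The sizes rest on X being enrolment date, uniform accrual, no random loss, and assumed diagnosis-time and exit patterns. The IPG model has the same form and is open to the same mechanism, but it was not simulated, so no size is claimed for it.

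**What to change.** In SAP 8.2.1:

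- Define X as calendar date of enrolment for SND, and of diagnosis for IPG.
- For SND, set Y = diagnosis within 6 months of enrolment and Z = time to diagnosis, exit or 6 months, whichever is first. Scheduled follow-up is at least 6 months, except at catch-up centers, where Protocol 4.3 makes 6 months the maximum.
- For IPG, set Y = implant within 3 months of diagnosis, truncate Z in the same way, and restrict to subjects diagnosed at least 3 months before data cut-off.
- Read a β1 association as evidence of drift only from this model.
- Because Z still ends at exit, a change in exit timing between phases could bias β2. Also report the fixed-window proportion version with all enrolled subjects as denominator, using robust standard errors.

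In simulation the SND window model gives β1 rejection of 4.4-5.6% and median exp(β2) of 0.99-1.02 with no effect. Under 20% to 28%, median exp(β2) is about 1.5, against a hazard ratio of ln(0.72)/ln(0.80) = 1.47. The proportion version with robust standard errors rejects in about 5%.

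The cost is SAP wording and a few lines of code, with no new data. Diagnoses after 6 months and implants after 3 months drop out of this sensitivity analysis only; they stay in the primary and time-to-event analyses.
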